7.1. Disposition of Subjects and Withdrawals

Disposition will include tabulations of the number of subjects enrolled (Cohort 1) and/or randomized (Cohort 2), the number of subjects rolled over from Cohort 1 to Cohort 2, the number of subjects who received treatment, tabulated reasons for discontinuation from the study, and number of subjects in each analysis population by treatment within cohort.

Percentages will be based on the number of subjects in the Safety Population for each cohort.

7.2. Protocol Violations and Deviations

All protocol deviations recorded by the site (classified as major or minor) will be listed.

7.3. Demographics and Other Baseline Characteristics

Summary statistics for age, gender, race, ethnicity, height, weight, and BSA will be presented by treatment within cohort.

For the continuous variables, the number of non-missing values and the mean, standard deviation, minimum, median, and maximum will be tabulated.

For the categorical variables, the counts and proportions of each value will be tabulated.

These analyses will be conducted for the Safety Population for each cohort.

The number and percent of subjects reporting various medical histories, grouped by MedDRA system organ class and preferred term, will be tabulated by treatment within cohort. This analysis will be conducted for the Safety Population for each cohort.

Subjects rolling over from Cohort 1 into Cohort 2 will have demographics and baseline characteristics tabulated for both cohorts.

7.4. Exposure and Compliance

The number of doses received by each subject based on diary data will be summarized by treatment for Cohort 2 subjects only, in both a continuous manner (using summary statistics) and a categorical manner (using number and percentages), presenting the following categories: 1 to 8 doses (up to 1 week of treatment); 9 to 15 doses (1-2 weeks of treatment); 16-23 doses (2-3 weeks of treatment); and 24 to 31 doses (3-4 weeks of treatment).

Similarly, the amount of study medication applied by each subject based on tube weight will be summarized by treatment for Cohort 2 subjects only, using summary statistics.

These analyses will be conducted for the Safety Population for each cohort.

AD-ST-33.04 Effective date: 30-Jun-2017

Drug application for each cohort, vehicle training application for Cohort 2, study medication dispensation and return weight, and missed doses will be presented in the listings.

8. Efficacy Analysis

Efficacy will be assessed for Cohort 2 only. Individual subject listings will be prepared for all efficacy data.

8.1. Primary Efficacy Analysis

The primary efficacy endpoint is difference in mean percent change from baseline at Week 4 in the product of TPSS x TPA between each dose concentration level of ARQ-151 cream and vehicle control. This will be assessed as a sum of up to 3 target plaques per subject.

The primary endpoint will be analyzed using a mixed model for repeated measures (MMRM), with center within country, treatment, study visit, and treatment-by-study visit interaction as fixed effects and baseline TPSS x TPA score as a covariate. In comparing the visit value to baseline within each treatment group, least squares (LS) mean percent change from baseline will be presented along with associated 95% confidence interval (CI). In comparing treatments (ARQ-151 minus Vehicle), LS mean differences in percent change from baseline will be presented along with associated 95% CI and pairwise treatment *P* value. An unstructured covariance structure will be used, unless the model does not converge; in that case, the appropriate covariance structure will be investigated. Possible covariance structures include autoregressive (AR [1]), compound symmetry (CS), and variance components (VC) with each model fit to find the covariance structure with the best fit. The fit statistics will be compared for all covariance structures; the structure with the smallest Akaike information criterion will be retained as the preferred model.

The Bonferroni method will be used to control for multiplicity, where the significance level for each of the 2 comparisons of active versus placebo is $\alpha = 0.025$.

Descriptive statistics for absolute and percent change from baseline at Week 4 will be presented by treatment group.

The primary efficacy analysis will be based on the mITT Population. This analysis will be repeated for the PP Population.

As a sensitivity analysis, the primary endpoint will be analyzed using an analysis of covariance (ANCOVA) with factors for center within country and treatment as fixed effects and baseline TPSS x TPA score as a covariate.

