9.1 Statistical Methods

The methodology presented below is a summary of the more detailed analysis plan that will be presented in the Statistical Analysis Plan (SAP). The SAP will be finalized before the database is locked and unblinded for Cohort 2. Any changes to the methods described in the final SAP will be described and justified in the clinical study report.

All statistical processing will be performed using SAS® (Version 9.4) unless otherwise stated. No interim efficacy analyses are planned.

Descriptive statistics will be used to provide an overview of the efficacy, safety and pharmacokinetic results. For categorical parameters, the number and percentage of subjects in each category will be presented. The denominator for percentage will be based on the number of subjects appropriate for the purpose of analysis. For continuous parameters, descriptive statistics will include n (number of subjects), mean, standard deviation (SD), median, minimum, and maximum.

P-values of less than 0.05 will be considered statistically significant based on a two-sided test unless otherwise specified.

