4.1. Introduction

Data processing, tabulation of descriptive statistics, calculation of inferential statistics, and graphical representations, except for PK parameter estimation, will be performed primarily using SAS (release 9.4 or higher). All PK parameter estimations will be performed using WinNonlin® version 6.4 or later. If the use of other software is warranted, the final statistical methodology report will detail what software was used for what purposes.

For purposes of this SAP, “treatment within cohort” is defined as enrolled subjects (“Overall”) for Cohort 1 and treatment group (“ARQ-151 0.5%,” “ARQ-151 0.15%,” and “Vehicle”) for Cohort 2. For background and efficacy summaries for Cohort 2, this will be the randomized (ie, planned) treatment group; for safety summaries, this will be the actual (ie, received) treatment group.

Where possible, data for both cohorts will be summarized in the same output.

Continuous (quantitative) variable summaries will include the number of subjects (n) with non-missing values, mean, standard deviation (SD), median, minimum, and maximum.

Categorical (qualitative) variable summaries will include the frequency and percentage of subjects who are in the particular category or each possible value. In general, the denominator for the percentage calculation will be based upon the total number of subjects in the study population for the treatment groups within cohort, unless otherwise specified.

The minimum and maximum will be reported with the same degree of precision (ie, the same number of decimal places) as the observed data. Measures of location (mean and median) will be reported to 1 degree of precision more than the observed data and measures of spread (SD) will be reported to 2 degrees of precision more than the observed data.

Percentages will be presented to 1 decimal place, unless otherwise specified.

Unless otherwise indicated, all statistical tests will be conducted at the 0.05 significance level using 2-tailed tests, and *p* values will be reported. Corresponding 95% confidence intervals (CIs) will be presented for statistical tests.

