6.1.3. Multiple Comparisons

The type I error rate of $\alpha = 0.05$ will be maintained for the entirety of the primary endpoint by using the Bonferroni method to control for multiplicity, where the significance level for each of the 2 comparisons of active versus placebo is $\alpha = 0.025$.

No adjustments will be made for multiple comparisons for other endpoints; all analyses will be conducted at the $\alpha = 0.05$ level.

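### The two primary Week 4 comparisons are tested at two-sided 0.025 but reported with 95% confidence intervals; the interval that matches the test is 97.5%

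*SAP*

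**What the plan says.** SAP 8.1 specifies an MMRM for percent change from baseline in TPSS x TPA. For the active-minus-vehicle contrasts it states that "LS mean differences in percent change from baseline will be presented along with associated 95% CI", together with a pairwise p-value. The same section then says "The Bonferroni method will be used to control for multiplicity, where the significance level for each of the 2 comparisons of active versus placebo" is 0.025. SAP 6.1.3 gives the purpose: the overall 0.05 error rate "will be maintained for the entirety of the primary endpoint by using the Bonferroni method to control for multiplicity". Protocol 9.2.1 repeats the 0.025 level and gives no confidence level.

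The general rule is in SAP 4.1: "Unless otherwise indicated, all statistical tests will be conducted at the 0.05 significance level using 2-tailed tests". It continues: "Corresponding 95% confidence intervals (CIs) will be presented for statistical tests". The opening words of the rule let the test level differ from 0.05. The sentence on intervals has no such exception. Protocol 9.1 is also two-sided: "P-values of less than 0.05 will be considered statistically significant based on a two-sided test unless otherwise specified".

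SAP 8.1 adds two further analyses of the primary endpoint. For the per-protocol set it says "This analysis will be repeated for the PP Population". It also plans an ANCOVA as a sensitivity analysis. No 97.5% or multiplicity-adjusted interval appears in the text available for either document.

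**The concern.** A two-sided test at level α rejects exactly when the 100(1 − α)% interval excludes zero. At α = 0.025 that interval is 97.5%, not 95%. With 95% intervals, a result with p between 0.025 and 0.05 appears in the primary table as an interval that excludes zero beside a comparison that has failed. A reader who judges from the interval, as many do, would draw the opposite conclusion from the plan's decision rule.

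The multiplicity protection described in SAP 6.1.3 also stops at the p-values. It does not carry over to the pair of intervals printed with them.

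**Working it through.** **Inputs.** 24 per arm, difference 23 points, SD 25 points, α = 0.025, 80% power, 16% dropout and 84 subjects in total (Protocol 9.1.1, SAP 3.2); 1:1:1 allocation (SAP 3.5); two comparisons at 0.025 each (SAP 8.1). The calculations use a simple contrast of two arms with the SD pooled over three arms, not the planned MMRM.

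**Step 1: reproduce the plan's power and settle sidedness.** SAP 8.1 does not itself say whether 0.025 is one- or two-sided. This matters, because a 95% interval would match a one-sided 0.025 test.

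- SE = 25 × √(2/24) = 7.217; noncentrality = 23 / 7.217 = 3.19.
- Error df = 3 × 23 = 69 (pooled over three arms), or 46 using two arms only.

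| Reading of 0.025 | Power, 69 df | Power, 46 df | n per arm for 80% (t) |
|---|---|---|---|
| Two-sided | 81.3% | 80.5% | 24 |
| One-sided | 88.1% | 87.7% | 20 |

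Only the two-sided reading gives 24 per arm, and it agrees with SAP 4.1 and Protocol 9.1. A three-arm omnibus F test at 0.025 does not fit either: it gives 71% or 85%, depending on where the third mean lies.

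**Step 2: matching confidence level.** 100 × (1 − 0.025) = 97.5%.

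**Step 3: half-widths.**

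- 24 per arm, 69 df: 95% gives 1.9949 × 7.217 = 14.40 points; 97.5% gives 2.2914 × 7.217 = 16.54 points. The ratio is 1.149.
- 28 per arm (84/3, all randomised subjects analysed), 81 df: SE = 25 × √(2/28) = 6.682; the half-widths are 1.9897 × 6.682 = 13.29 and 2.2838 × 6.682 = 15.26 points.

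With 24 per arm and the observed SE at its planning value, an observed difference between 14.4 and 16.5 points in absolute value has a 95% interval that excludes zero but fails the 0.025 test.

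**Step 4: chance of that conflict, per comparison.** This is the probability of rejecting at two-sided 0.05 minus that at two-sided 0.025 (noncentral t).

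| True difference | n per arm | Reject at 0.05 | Reject at 0.025 | Conflict |
|---|---|---|---|---|
| 23 | 24 | 88.15% | 81.25% | 6.9% |
| 23 | 28 | 92.52% | 87.44% | 5.1% |
| 0 | 24 | 5.0% | 2.5% | 2.5% |

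The chance is higher when the true difference lies near the critical values: 11.5% at a true difference of 16 points with 24 per arm.

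**Step 5: the two intervals together.** The contrasts share the vehicle arm (correlation 0.5). Simulation with 4,000,000 draws and pooled SD gives these joint coverages (Monte Carlo SE below 0.0002):

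| n per arm | Both 95% | Both 97.5% |
|---|---|---|
| 24 | 90.97% | 95.39% |
| 28 | 90.95% | 95.36% |

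If the intervals were read as tests, a normal approximation puts the familywise error at 9.1% with 95% intervals and 4.6% with 97.5% intervals, against the intended 5%.

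**The case against.** The best defence is that the decision rule is complete without the interval. The p-value is printed beside it, is compared with 0.025, and no section uses a confidence limit to declare success. Unadjusted 95% intervals next to Bonferroni-tested p-values can be a deliberate display choice, and each is valid on its own terms. The word used in SAP 4.1 to link intervals and tests may mean only that an interval accompanies each test. The documents promise control of the type I error, not joint coverage, so 91% is a consequence rather than a missed target. One MMRM table also carries Weeks 1 to 3, where the contrasts are tested at 0.05 and 95% is the matching level. The 97.5% limits can be recovered from the estimate, the 95% limits and the degrees of freedom. Finally, the table shells were removed from the public SAP, so a footnote or an extra column there cannot be ruled out.

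Most of this stands, and it is why the point is minor. It does not remove the mismatch. SAP 8.1 names 95% expressly for contrasts that the same section tests at 0.025, and it asks for no label saying that the interval is unadjusted. The case for a uniform 95% covers Weeks 1 to 3 and the secondary endpoints, not the two Week 4 primary contrasts.

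**Conclusion.** The concern holds, as a minor reporting mismatch on the primary result. The two Week 4 contrasts are tested at two-sided 0.025 and reported with intervals that match a two-sided 0.05 test. The test, its error rate, the power, the estimates and each interval's marginal 95% coverage are sound. What fails is agreement between interval and decision when p lies between 0.025 and 0.05.

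The sizes rest on the planning SD of 25 and on a simple pooled-SD contrast. The MMRM, with its baseline and center terms, will have a different standard error and degrees of freedom. The ratio of the two half-widths should change little: it is 1.144 in the normal limit and 1.149 at 69 df. That 97.5% is the matching level does not depend on these assumptions; it needs only the two-sided reading, which the text and the sample size both support.

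**What to change.** Add to SAP 8.1, with a matching exception in SAP 4.1:

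> *For the two Week 4 active-minus-vehicle contrasts in TPSS x TPA, two-sided 97.5% CIs will be presented, matching the 0.025 level of each test; 95% CIs may be shown alongside as unadjusted.*

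Apply the same to the Week 4 contrasts in the per-protocol repeat and the ANCOVA, so that they can be compared with the primary result on the same footing. Keep 95% for within-group LS means and for the secondary endpoints, which are tested at 0.05. Labelling the existing 95% intervals as unadjusted for multiplicity would prevent the misreading, but would still leave the primary test without its matching interval.

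The cost is one sentence and one exception. The primary intervals become about 15% wider (half-width 16.5 instead of 14.4 points at planning values). Two confidence levels will appear in the efficacy output, so each interval must state its level. Sample size, power, estimates and tests do not change.

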9.1.1 Determination of Sample Size

A sample size of 24 per arm (72 total) will provide 80% power to detect a difference of 23% in the mean percent change from baseline in TPSS x target plaque area (cm^2) between the ARQ-151 cream and the matching vehicle arms, with a standard deviation for the change of 25%. This is based on a one-way analysis of variance (ANOVA) at the $\alpha = 0.025$ significance level. With a 16% dropout rate, the sample size for the study would be increased to 84 subjects.

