9.2.1 Primary Efficacy Endpoint

In the parallel group assessment (Cohort 2), the Primary Efficacy Endpoint will be the Difference in mean percent change from baseline at week 4 in TPSS x TPA between each dose concentration level of ARQ-151 cream and vehicle control. This will be assessed as a sum of up to 3 target plaques per subject.

The primary endpoint will be analyzed using a mixed model for repeated measures (MMRM), with center, treatment, study visit, and study visit-by-treatment interaction as fixed effects and baseline TPSS x TPA score as a covariate. An unstructured covariance structure will be used, unless the model does not converge; in that case, the appropriate covariance structure will be investigated. The Bonferroni method will be used to control for multiplicity, where the significance level for each of the two comparisons of active versus placebo is $\alpha=0.025$.

Descriptive statistics for absolute and percent change from baseline at Week 4 will be provided.

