6.1.7. Derived Variables

- TPSS = sum of erythema (graded 0-4), thickness (graded 0-4), and scaling (graded 0-4) for each target plaque. The sum of TPSS scores of up to 3 target plaques within a visit will be used for analysis.
- TPA (cm^2) = the longest diameter (cm) of the target plaque multiplied by the widest perpendicular diameter (cm) (ie, perpendicular to the longest diameter of the target plaque). The sum of TPA (cm^2) of up to 3 target plaques within a visit will be used for analysis.
- TPSS x TPA = sum of TPSS x TPA of up to 3 target plaques within a visit. Note that TPSS x TPA is calculated for each target plaque before summing up the results for all plaques. If a plaque is resolved after baseline with a score of 0 for all descriptors for TPSS (ie, erythema, thickness, and scaling), TPSS x TPA will be recorded as 0.
- Cream used (g) in a tube = dispensed tube weight (g) – returned tube weight (g).
- Overall cream used (g) = sum of cream used in a tube over all tubes
- Number of doses of study drug = number of expected doses (number of days on study [including BID dosing on Days 1, 14, and 28], where number of days on study is derived as last treatment – first treatment + 1) minus total number of missed doses, as collected in the CRF. Add a 1 for each of the Day 1, 14, and 28 visits that are completed (meaning, study drug discontinuation did not occur until at least the next day; so if a subject finished the study, 3 doses would be added to the final amount).
- Percent compliance (for purposes of determining the PP Population as described in [Section 5](#)) = average of compliance as recorded in the eCRF, calculated as sum of [100% if “Was the subject compliant?” marked Yes in the eCRF or percent compliance as recorded in the eCRF comments when “Was the subject compliant?” is marked as No] / number of non-missing compliance records from the eCRF.
- Quick Inventory of Depressive Symptomatology-Self-Report (QIDS-SR) total score = (highest score on questions 1-4) + item 5 + (highest score on questions 6-9) + item 10 + item 11 + item 12 + item 13 + item 14 + (highest score on questions 15-16). The range for the QIDS-SR total score is 0 to 27.

- QIDS-SR severity level⁴:
 - No depression: total score ≤ 5
 - Mild depression: total score = 6 to 10
 - Moderate depression: total score = 11 to 15
 - Severe depression: total score = 16 to 20
 - Very severe depression: total score ≥ 21

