8.2. Secondary Efficacy Analysis

The secondary efficacy endpoints for Cohort 2 include the following:

AD-ST-33.04 Effective date: 30-Jun-2017

1. Difference in mean percent change from baseline at weeks 1, 2, and 3 in TPSS x TPA between each dose concentration level of ARQ-151 cream and vehicle control.
2. Difference in mean percent change from baseline at weeks 1, 2, 3, and 4 in TPSS between each dose concentration level of ARQ-151 cream and vehicle control.
3. Difference in mean percent change from baseline at weeks 1, 2, 3, and 4 in TPA between each dose concentration level of ARQ-151 cream and vehicle control.

Each of the secondary efficacy endpoints will be analyzed using MMRM methods similar to the primary endpoint; however, no adjustments for multiplicity will occur, and all analyses will be conducted at the $\alpha = 0.05$ level.

Additionally, descriptive statistics for absolute and percent change from baseline to each week (ie, Weeks 1, 2, 3, and 4) will be presented by treatment group.

9. Safety and Tolerability Analysis

Safety will be evaluated from reported AEs, application site reaction assessments, physical examinations, and changes in clinical laboratory values, vital signs, and 12-lead ECGs.

Descriptive statistics will be calculated for quantitative safety data and frequency counts will be compiled for classification of qualitative safety data. No formal inferential statistics will be performed on safety assessments. Individual subject listings will be prepared for all safety data.

All safety analyses will be performed on the Safety Population for each cohort. All safety data will be presented in the listings.

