13.1.2. Efficacy Data

Table 6: Efficacy Data Summary Tables

Number	Population	Title
Table 14.2.1.1.1	mITT	Summary of Target Plaque Severity Score (TPSS) x Target Plaque Area (TPA) (cm ²) by Study Visit and Treatment
Table 14.2.1.1.2	mITT	Percent Change from Baseline in Target Plaque Severity Score (TPSS) x Target Plaque Area (TPA) (cm ²) by Study Visit and Treatment, Tabulation of Fitted Summary Statistics from MMRM
Table 14.2.1.2.1	PP	Summary of Target Plaque Severity Score (TPSS) x Target Plaque Area (TPA) (cm ²) by Study Visit and Treatment
Table 14.2.1.2.2	PP	Percent Change from Baseline in Target Plaque Severity Score (TPSS) x Target Plaque Area (TPA) (cm ²) by Study Visit and Treatment, Tabulation of Fitted Summary Statistics from MMRM
Table 14.2.1.3	mITT	Percent Change from Baseline in Target Plaque Severity Score (TPSS) x Target Plaque Area (TPA) (cm ²) by Study Visit and Treatment, Tabulation of Fitted Summary Statistics from ANCOVA
Table 14.2.2.1	mITT	Summary of Target Plaque Severity Score (TPSS) by Study Visit and Treatment
Table 14.2.2.2	mITT	Percent Change from Baseline in Target Plaque Severity Score (TPSS) by Study Visit and Treatment, Tabulation of Fitted Summary Statistics from MMRM
Table 14.2.3.1	mITT	Summary of Target Plaque Area (TPA) (cm ²) by Study Visit and Treatment
Table 14.2.3.2	mITT	Percent Change from Baseline in Target Plaque Area (TPA) (cm ²) by Study Visit and Treatment, Tabulation of Fitted Summary Statistics from MMRM

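### SAP 8.1: the fallback covariance structures named for the primary MMRM all assume one variance for Weeks 1-4; add heterogeneous versions (minor, rarely triggered)

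*SAP*

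**What the plan says.** Protocol 9.2.1 sets the rule for the primary model: "An unstructured covariance structure will be used, unless the model does not converge; in that case, the appropriate covariance structure will be investigated". It names no fallback, which is acceptable because Protocol 9.1 leaves detail to the SAP.

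SAP 8.1 repeats the rule and adds candidates: "Possible covariance structures include autoregressive (AR [1]), compound symmetry (CS), and variance components (VC"). It then fixes the choice: "the structure with the smallest Akaike information criterion will be retained as the preferred model". The list is introduced as a set of possibilities, so it is open. No heterogeneous-variance or Toeplitz structure is named in either document.

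SAP 8.2 carries the approach over: "Each of the secondary efficacy endpoints will be analyzed using MMRM methods similar to the primary endpoint". These endpoints are tested week by week at 0.05 without adjustment.

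SAP 8.1 also plans an ANCOVA of the primary endpoint as a sensitivity analysis. In Table 6 of SAP 13.1.2 the ANCOVA appears once, for TPSS x TPA in the mITT population, in a table titled "by Study Visit and Treatment, Tabulation of Fitted Summary Statistics from ANCOVA". TPSS alone and TPA alone have MMRM tables and descriptive tables, but no ANCOVA.

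**The concern.** The primary test concerns one visit, Week 4, with each dose compared with vehicle at 0.025. An unstructured matrix gives Week 4 its own variance. AR(1), CS and VC, read as ordinary within-subject structures, replace it with one variance pooled over the four weeks. AIC ranks only the candidates it is given, so it cannot repair this if all of them share the restriction.

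Nothing in the documents supports equal variances by week. The sample size section gives a single value, "with a standard deviation for the change of 25" percent, and no weekly SDs. SAP 6.1.7 gives a reason why spread might change: for a plaque resolved after baseline, "TPSS x TPA will be recorded as 0". That could shrink late spread, although it does not settle the direction.

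If the fallback were used, rising spread would push the Week 4 error above its nominal level, and falling spread would cost power. Even where Week 4 happens to be right, other weeks, which are secondary endpoints, can be wrong.

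**Working it through.** **Inputs from the documents.** Three arms, 1:1:1; difference 23 points; SD 25; 24 per arm for 80% power, raised to 84 in total for 16% dropout (Protocol 9.1.1, SAP 3.2). Two comparisons at 0.025 (SAP 6.1.3), two-sided (SAP 4.1). Four post-baseline visits (Protocol 8.13.1).

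**The plan's own figure.** n per arm = 2(z₀.₉₈₇₅ + z₀.₈₀)² × 25²/23² = 2(2.241 + 0.842)² × 625/529 = 22.5, so 23 by the normal approximation. With the noncentral t, 23 per arm gives 78.5% (two-arm df) or 79.4% (three-arm df), and 24 gives 80.5% or 81.2%. The stated 24 is reproduced.

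**Size of the effect if a one-variance structure is used.** With complete data the Week 4 contrast takes its standard error from the pooled SD:

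- SE ratio = √[(SD₁² + SD₂² + SD₃² + SD₄²)/4] / SD₄
- error per comparison = 2[1 − Φ(2.241 × SE ratio)]
- family-wise error: the two contrasts share the vehicle arm, so their correlation is 0.5.

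Example, 15/20/23/25: √[(225 + 400 + 529 + 625)/4] = √444.75 = 21.09. The ratio is 21.09/25 = 0.84.

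| Assumed SDs, Weeks 1-4 | SE ratio, Week 4 | Error per comparison (nominal 0.025) | Family-wise error |
|---|---|---|---|
| 25/25/25/25 | 1.00 | 0.025 | 0.047 |
| 20/22/24/25 | 0.91 | 0.041 | 0.074 |
| 15/20/23/25 | 0.84 | 0.059 | 0.106 |
| 25/25/22/18 | 1.26 | 0.005 | 0.009 |
| 20/29.2/25/25 | 1.00 | 0.025 | 0.046 |

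In the last row Week 4 is right, but the pooled SD of 25.01 is 1.25 times the Week 1 SD and 0.86 times the Week 2 SD. At an unadjusted 0.05 that gives errors of 0.014 at Week 1 and 0.093 at Week 2.

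**Simulation with the fallback forced.** 28 per arm, 8 centers, baseline covariate, 16% monotone dropout, AR correlation 0.75, REML with Kenward-Roger tests, 2,000 trials per row, Monte Carlo SE about 0.005. Entries are Week 4 family-wise error.

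| Assumed SDs | AIC among AR(1), CS, VC | AIC with heterogeneous AR(1), CS, Toeplitz added | Unstructured |
|---|---|---|---|
| Equal | 0.050 | 0.049 | 0.050 |
| 20/22/24/25 | 0.073 | 0.045 | 0.042 |
| 15/20/23/25 | 0.113 | 0.050 | 0.048 |
| 25/25/22/18 | 0.009 | 0.037 | 0.038 |
| 20/29.2/25/25 | 0.050 | 0.042 | 0.040 |

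For 15/20/23/25 the model SE divided by the empirical SD at Week 4 was 0.83 with the named three and 0.99 with six. For 25/25/22/18, power for 23 points was 93.0% v 97.5%. For 20/29.2/25/25, error per comparison at unadjusted 0.05 was 0.019 (Week 1) and 0.099 (Week 2), v 0.048 and 0.047.

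**Other simulations.** One with 24 per arm, complete data and heterogeneous AR(1) and CS added gave, per comparison, 0.047 v 0.021 for 15/20/23/25. For 20/22/24/25 it gave 0.026 v 0.023 (800 replicates, no clear change), although the SE ratio improved from 0.91 to 0.97. A further one with the same two additions gave family-wise 0.098 v 0.034 (15/20/23/25, SE ratio 0.84), 0.008 v 0.033 (25/25/22/18, SE ratio 1.25), 0.057 v 0.040 (20/22/24/25) and 0.038 v 0.037 (equal SDs).

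**How often the fallback is reached.** Unstructured has 10 covariance parameters for four visits, against 72 to 84 subjects. It converged in all 13,998 estimable simulated data sets, including stress cases with 50% dropout. For 15/20/23/25, each 1% chance of non-convergence adds 0.01 × (0.1126 − 0.0475) ≈ 0.0007 to the overall error.

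**The case against.** The strongest reply is that the plan contains no error. The primary model is right. The fallback wording leaves the choice open, so a heterogeneous structure is already allowed and the AIC rule would cover it. The trigger never fired in simulation. All error rates come from forcing the fallback on data where the unstructured model had converged, so they are not conditional on real non-convergence, and nothing shows that heterogeneous Toeplitz (7 parameters) would converge when unstructured fails. The weekly SDs are assumed. The planned ANCOVA checks TPSS x TPA and, from its table title, may cover Weeks 1-3 as well, although SAP 8.1 ties it to the primary endpoint.

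All of this stands, and it sets the weight of the point. It does not remove it: SAP 8.1 names candidates, and each named one gives wrong standard errors when visit variances differ. The mild profile 20/22/24/25 is uncertain, because the simulations disagree on how far its error rate moves. The steeper profile and the falling profile are consistent between formula and simulation.

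A reader might infer that the primary analysis runs at a family-wise error near 0.11. The documents do not support that: the figure needs non-convergence, a choice confined to the named structures, and one assumed SD profile. A reader might also infer that VC should be struck out because AIC never chose it in the main simulation. That only reflects the simulated correlations of 0.75 and 0.97; VC assumes none, and keeping it under an AIC rule does no harm.

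**Conclusion.** This is a minor, cheap improvement to a contingency rule and not a defect in the primary analysis. If the fallback is reached and the choice stays within AR(1), CS and VC, the Week 4 standard error is about 16-17% too small for assumed SDs 15/20/23/25, about 25% too large for 25/25/22/18, and right for equal SDs. The direction in this trial cannot be known from the documents. The result rests on assumed weekly SDs, on VC being used as a within-subject structure without grouping, and on simulations in which the fallback was imposed.

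For TPSS x TPA the ANCOVA would help expose a distorted Week 4 result. TPSS and TPA alone have no such second model, which is why the list should also cover the secondary analyses.

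**What to change.** Before unblinding, add heterogeneous AR(1), heterogeneous CS and heterogeneous Toeplitz to the fallback list in SAP 8.1. Keep the smallest-AIC rule, applied among the structures that converge. State in SAP 8.2 that the same list applies to the secondary MMRMs. VC can stay. Naming the structures now also means that a later choice of an unlisted one cannot look data-driven.

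The cost is a sentence or two in the SAP. Heterogeneous AR(1) and CS each add three variance parameters to their one-variance forms; heterogeneous Toeplitz adds two further correlations. If the variances are in fact equal and the fallback is used, simulated power for the planned difference falls from 79.6% to 79.1%, about half a percentage point. Sample size, endpoints and the primary model do not change.
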